**VENTILATOR-INDUCED LUNG VORTEX IN
PATIENTS WITH SARS-CoV-2**

NCT04174313

MARCH 25, 2020

Materials and method

This study was conducted in the ICU dedicated to COVID-19 patients of an intensive care unit at a university hospital in Argentina. Approval was obtained from local institutional review board (resolution number: 68/2019) and informed consent followed the ethical committee's recommendations.

Inclusion criteria: This single-center prospective observational study evaluated consecutively admitted adult patients who were suffering from ARDS secondary to COVID-19 and needed volume-controlled ventilation (VCV) for at least 7 days. These eligibility criteria were decided in order to allow a minimum monitoring of the mechanical variables. Those who did not meet such requirement were excluded.

ARDS was defined according to the Berlin criteria (19) while the diagnosis of COVID-19 pneumonia was established based on CT images showing such condition and on real-time polymerase chain reaction (RT-PCR) test for coronavirus disease-2019.

Exclusion criteria: Patients with do-not-resuscitate (DNR) orders and pregnant women. Cardiac arrest before ICU admission. Extra corporeal membrane oxygenation (ECMO) requirement within the first 24 h of ICU admission and chronic obstructive pulmonary disease with gold class 3 or 4, or home oxygen therapy (20).

Procedure: Patients were administered sedatives and analgesics (propofol and fentanyl) to obtain a score of -5 on the RASS scale. The protective ventilatory strategy included: low tidal volume ventilation (6 ml/kg/PBW), plateau pressure limitation (Pplat: <30 cmH₂O) and prone positioning for severe hypoxemia (21). FiO₂ and PaCO₂ were adjusted to achieve SaO₂ between 92 and 96% and pH >7.20, respectively. PEEP was titrated according to the best compliance of the respiratory system (CRS), without exceeding the Pplat limit set. Neuromuscular blockers were administered to patients suffering from severe ARDS (PaO₂/FiO₂ <100) and to the ones with hypoxemia associated with asynchronies despite the administration of sedoanalgesia, Pplat >32 cmH₂O or that needed prone positioning to improve oxygenation.

Mechanical variables and PaO₂/FiO₂ were registered daily for 14 days or until initiating assisted ventilation. These data were obtained in passive mechanical conditions.

Ventilator-induced lung injury vortex was defined as a progressive increase in driving pressure (ΔP) as Vt remained constant or even decreased.

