Refractory hypoxemia was defined as PaO₂/FiO₂ <100 despite the optimization of mechanical ventilation and prone positioning.

Respiratory mechanics: Peak airway pressure, plateau pressure, and total PEEP were measured. The value of driving pressure (ΔP : Pplat - PEEP total), static compliance of the respiratory system (CRS = Vt/ ΔP) and specific mechanical power (SMP: mechanical power/CRS) were calculated. Mechanical power was computed as: Peak airway pressure x Vt - (ΔP x Vt/2) x respiratory rate x 0.098 (13).

Complications: The following variables and complications were also observed during the period of analysis: incidence of pneumonia associated with mechanical ventilation (14), need for noradrenaline over 0.1 μ g/kg/min for more than 24 h, positive blood cultures, accumulated fluid balance, dialysis treatment, clinical and/or

echocardiographic evidence of heart failure, lactate ≥ 2 mmol/L in at least two consecutive samples, presence of persistent fever ($\geq 38^\circ$ at least once a day for three consecutive days), and the highest value of ferritin, D-dimer, C-reactive protein, troponin I and LDH obtained during the first 14 days of invasive mechanical ventilation.

Statistical analysis: Dichotomic data are reported as frequencies and percentages while continuous data are presented as mean (standard deviation) or median (interquartile range) as appropriate, depending on the normality of distribution. Kolmogorov–Smirnov test was used to test normality of distribution for continuous variables. Comparisons between the two groups (VILI vortex vs. No VILI vortex) and intragroup (day: 7 vs. day: 14) were analyzed by either an independent t-test or the Mann–Whitney test. Differences in categorical variables were assessed using the χ^2 or Fisher's exact test.

The mortality predictive model following refractory hypoxemia as well as mortality for any reason was analyzed on day 90 by means of ROC curves. Survival difference between both groups was analyzed through longrank test. Cox's proportional hazards regression test was used to study the relationship between VILI vortex intensity and accumulative risk of death from refractory hypoxia. The difference of driving pressure ($\Delta\Delta P$) between days 7 and 14 was regarded as VILI vortex intensity expression. That was the period in which we more frequently observed VILI vortex development.

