Data analysis was conducted with MedCalc 11.4.3.0 statistical software (Mariakerke, Belgium) and a p-value of <0.05 was considered statistically significant.

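### Cox regression of ΔΔP on the accumulative risk of hypoxemic death leaves other-cause deaths unaddressed; if they are censored, the hazard ratio does not by itself describe cumulative risk

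*Combined protocol and SAP*

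**What the plan says.** All the relevant text is in the Statistical analysis section.

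- **Main model.** Cox's "proportional hazards regression test was used to study the relationship between VILI vortex intensity and accumulative risk of death from refractory hypoxia".
- **Exposure.** Intensity is ΔΔP: the change in driving pressure "between days 7 and 14 was regarded as VILI vortex intensity expression".
- **Other mortality outcomes.** "The mortality predictive model following refractory hypoxemia as well as mortality for any reason was analyzed on day 90 by means of ROC curves". The predictor in these ROC curves is not named. Day 90 is stated here only, not for the Cox model or the log-rank test.
- **Group comparison.** "Survival difference between both groups was analyzed through longrank test". The groups are vortex and no vortex, and no cause of death is named.

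The section gives no rule for deaths from other causes in the Cox model. It names no cumulative incidence estimate, Gray's test or Fine-Gray model, and no time-to-event model of ΔΔP for other-cause or all-cause death.

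**The concern.** The Cox outcome is one cause of death. Because the plan lists any-cause mortality separately, it recognises deaths that fall outside that outcome. A patient who dies of something else can no longer die of refractory hypoxemia, so those deaths are competing events.

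With other-cause deaths censored, Cox regression estimates how ΔΔP relates to the rate of hypoxemic death among patients still alive. That is a legitimate question. The plan, however, states its target as accumulated risk: the proportion of patients who go on to die this way. That proportion depends on two things: the effect of ΔΔP on hypoxemic death, and its effect on the deaths that remove patients first. The plan models only the first against ΔΔP. A reader given the hazard ratio alone could not tell how far the actual risk of hypoxemic death rises with vortex intensity.

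**Working it through.** The documents state no sample size, event count, mortality or hazard ratio, so there is no figure of the plan's to reproduce. What follows is an illustration, and every input is assumed.

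**Setup.** Two proportional cause-specific hazards, no other censoring, follow-up from day 14 to day 90.

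- F = reference mortality; s = share of those deaths that are hypoxemic.
- H = −ln(1 − F).
- a = HR_hypoxemic × H × s; b = HR_other × H × (1 − s).
- Reference cumulative incidence of hypoxemic death = F × s.
- Cumulative incidence at higher intensity = a/(a + b) × (1 − exp(−(a + b))).

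The hazard ratios compare a higher with a reference intensity. No particular increment of ΔΔP is implied.

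**Central case.** F = 0.5, s = 0.5, HR_hypoxemic = 2. Then H = 0.693, a = 2 × 0.693 × 0.5 = 0.693, and the reference incidence is 0.5 × 0.5 = 25.0%. The cause-specific hazard ratio is 2 in every row.

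| HR_other | b | Cumulative incidence | Rise (points) |
|---|---|---|---|
| 0.5 | 0.173 | 46.4% | 21.4 |
| 0.8 | 0.277 | 44.4% | 19.4 |
| 1 | 0.347 | 43.1% | 18.1 |
| 1.25 | 0.433 | 41.6% | 16.6 |
| 2 | 0.693 | 37.5% | 12.5 |

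Check of the last row: a + b = 1.386, a/(a + b) = 0.5, 1 − exp(−1.386) = 0.75, and 0.5 × 0.75 = 37.5%.

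The spread is 8.9 points for HR_other between 0.5 and 2, and 2.8 points between 0.8 and 1.25.

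**Range.** HR_hypoxemic = 2, F from 0.30 to 0.70, s from 0.25 to 0.75.

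| HR_other range | Smallest spread | Largest spread |
|---|---|---|
| 0.5 to 2 | 2.4 points (F 0.30, s 0.75) | 17.1 points (F 0.70, s 0.43) |
| 0.8 to 1.25 | 0.7 points (F 0.30, s 0.75) | 5.5 points (F 0.70, s 0.42) |

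At s = 1 the spread is zero.

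**Different assumed rates.** Take reference incidences of 15% hypoxemic and 25% other death, with the hypoxemic hazard ratio fixed at 1.5. The risk ratio for hypoxemic death is 1.54, 1.44, 1.25, 1.10 or 0.97 when HR_other is 0.5, 1, 2, 3 or 4. The conclusion is the same. In this setting the direction is lost only at the most extreme value tried.

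**Dependence on coding.** In a simulation of the central case, censoring other-cause deaths gave a hazard ratio of about 2.0 whatever HR_other was. Keeping those patients at risk as non-events to day 90, with complete follow-up, gave 2.14, 1.92 and 1.62 for HR_other 0.5, 1 and 2. The second coding gives a subdistribution hazard ratio, which does follow cumulative incidence. The plan's text does not say which coding is meant. At HR_other = 1 the two results are close (2.0 and 1.92), which is why the issue is small when other deaths are unrelated to ΔΔP.

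**The case against.** **The wording may simply be loose.** The sentence speaks of studying a relationship, and the plan proposes no absolute risk or risk curve from the Cox model. A cause-specific Cox model is a proper choice for an association question. This stands: the use of Cox is not at fault, and if only association is meant, correcting the description removes the claim about cumulative risk. It does not supply the unstated coding of other-cause deaths.

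**Other analyses may fill the gap.** The ROC curves include any-cause mortality, and their unnamed predictor could be ΔΔP. Binary data are reported as percentages with group tests, and with complete follow-up to day 90 a plain proportion of hypoxemic deaths is the cumulative incidence. This stands in part. A ROC curve measures discrimination at a fixed time, the log-rank test compares groups rather than ΔΔP, and the plan does not say that the categorical tests cover cause of death.

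**The illustration is not evidence about this study.** That is correct. The larger spreads need other-death hazard ratios of 0.5 or 2, which nothing in the documents supports.

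**Stronger readings to avoid.** A reader might infer that the Cox model can give at best a cause-specific hazard ratio. The documents do not establish that, because the handling of other-cause deaths is unstated and one possible coding yields a subdistribution hazard ratio. A reader might also infer that the hazard ratio is invalid or its direction unreliable. With other deaths censored, it remains valid for the cause-specific question, and nothing in the documents suggests associations with other deaths strong enough to reverse the direction of the risk.

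**Conclusion.** The concern holds in a limited form. The plan aims at the accumulated risk of one cause of death, recognises that other deaths occur, and does not say how they enter the Cox model. Under the usual censoring, the hazard ratio is sound but incomplete for that aim, and the other planned analyses only partly make up the difference.

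The size in this study cannot be determined. It is zero if every death is hypoxemic and small if other deaths are few or unrelated to ΔΔP. Under the assumed inputs, one hazard ratio of 2 leaves the cumulative risk uncertain by 0.7 to 5.5 points when the other-death hazard ratio lies between 0.8 and 1.25, and by 2.4 to 17.1 points when it lies between 0.5 and 2. These figures assume proportional cause-specific hazards and no other censoring. The point is a worthwhile, inexpensive improvement rather than a flaw that undermines the study.

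**What to change.** 1. Keep the Cox model. State that deaths from other causes are censored, and label the result a cause-specific hazard ratio.
2. Fit the same ΔΔP model for other-cause death and for all-cause death, and report the results together.
3. Where cumulative risk is claimed, report Aalen-Johansen cumulative incidence by vortex group with Gray's test, or a Fine-Gray model for continuous ΔΔP.
4. If cumulative risk is not intended, replace accumulative risk with cause-specific hazard and omit step 3.

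**Cost.** A little extra analysis, possibly in software other than the named package. It uses time and cause of death, which the planned analyses already need. If deaths are few, the other-cause estimates will be imprecise. As with the planned Cox model, every cause-specific result depends on how deaths are attributed to refractory hypoxemia.

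### The Cox model for 'vortex intensity' names no analysis set and no vortex term, so a plain vortex versus no-vortex difference can be read as an intensity effect

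*Combined protocol and SAP*

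**What the plan says.** All references are to the combined protocol and SAP.

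- **Vortex, yes or no** (Materials and method, Procedure). Vortex "was defined as a progressive increase in driving pressure (ΔP) as Vt remained constant or even decreased". No numeric threshold is given.
- **Intensity** (Statistical analysis). The driving-pressure difference ΔΔP "between days 7 and 14 was regarded as VILI vortex intensity expression". The definition is not limited to vortex patients or to positive values.
- **The model** (Statistical analysis). Cox's "proportional hazards regression test was used to study the relationship between VILI vortex intensity and accumulative risk of death" from refractory hypoxia. No other term, interaction or analysis set is named.
- **The yes/no contrast** (Statistical analysis). It appears only outside the Cox model: "Comparisons between the two groups (VILI vortex vs. No VILI vortex") are made by two-sample tests, and "Survival difference between both groups was analyzed through longrank test".
- **Who has a day-14 value** (Procedure). Mechanical variables "were registered daily for 14 days or until initiating assisted ventilation".

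**The concern.** ΔΔP can be computed for any patient with readings on days 7 and 14. Because vortex is defined by rising pressure, ΔΔP should be mostly positive in vortex patients and around zero or negative in the others. A single slope over everyone then combines three things: whether vortex is present, how far pressure rose in those who have it, and how far it fell in those who do not. Only the second is intensity. A no-vortex patient whose driving pressure falls by 3 cmH₂O enters with an intensity of −3.

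A significant hazard ratio could then be reported as more intense vortex, more death, even if the size of the rise carried no information. The evidence would be the vortex versus no-vortex difference that the log-rank test already examines, now expressed per cmH₂O.

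**Working it through.** **Inputs.** From the document: the definitions above, significance at p<0.05 (two-sided assumed), and day 90, which is stated for the ROC mortality analysis and assumed here for Cox. ΔΔP is known only at day 14, so time at risk is 90 − 14 = 76 days. The document gives no sample size, event rate, vortex share, ΔΔP distribution or hazard ratio (HR), so there is no planned figure to reproduce.

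Assumed: n = 60 or 100; vortex share 30 to 50%; ΔΔP = |Normal(4, SD 2)| with vortex and −|Normal(1, SD 2)| without; exponential survival times. ΔΔP has no effect on death within vortex patients.

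**Hand check of the mechanism.** These distributions have means of about 4.03 and −1.79, a gap of 5.82 cmH₂O. The variances are 20 − 4.03² ≈ 3.7 and 5 − 1.79² ≈ 1.8.

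- If only vortex status matters, with HR 3, a slope carrying the whole difference is ln 3 / 5.82 = 0.189 per cmH₂O.
- Spread within groups dilutes it. At a 50% share the between-group variance is 0.25 × 5.82² = 8.47 and the average within-group variance about 2.76. The factor is 8.47 / (8.47 + 2.76) = 0.75.
- Expected spurious HR: exp(0.189 × 0.75) ≈ 1.15 per cmH₂O. The simulated medians at HR 3 were 1.14 to 1.15.

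**Simulation 1: only vortex yes/no affects death.** Share of studies with p<0.05 for ΔΔP fitted alone in all patients:

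| Deaths without vortex (assumed) | Vortex HR (assumed) | n = 60 to 100 |
|---|---|---|
| 25% | 3 | 55–87% |
| 25% | 2 | 25–44% |
| 10% | 3 | 29–51% |
| 10% | 2 | 13–22% |
| 5% | 3 | 12–29% |
| 5% | 2 | 4–14% |

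The 25% rows use 500 or 600 replicates and vortex shares of 30 to 50%. The others use 400 replicates and a 40% share, with a Monte Carlo standard error of at most √(0.25/400) = 2.5 points. A repeat of the 10% rows gave 11 to 54%. With no effect of any kind the rate is 5 to 6%, so the excess comes from the group difference and not from a faulty test. At 25% mortality, ΔΔP within vortex patients was significant in about 4 to 7%.

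**Simulation 2: only the size of the fall in no-vortex patients affects death** (HR 1.3 or 1.5 per cmH₂O).

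| Model | Significant |
|---|---|
| ΔΔP alone, all patients | 21–61% |
| ΔΔP plus vortex yes/no | 9–23% |
| ΔΔP, vortex patients only | 4–5% |

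A simple vortex indicator is therefore not enough. In a separate run of 1,000 replicates per scenario, vortex yes/no plus ΔΔP recoded to 0 in no-vortex patients gave 4 to 7% here and 4 to 6% in the setting of Simulation 1 (HR 2 or 3).

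**What the within-vortex analysis can detect.** Assume a true HR of 1.2 per cmH₂O, vortex HR 3, 25% mortality without vortex and a 40% share. There are then about 14 (n = 60) or 23 (n = 100) deaths in vortex patients. Power ≈ Φ(ln 1.2 × √(deaths × 3.7) − 1.96), which gives Φ(−0.65) ≈ 26% and Φ(−0.28) ≈ 39%. Simulation gave 26% and 39%, and 13% and 21% at 10% mortality.

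**The case against.** **The plan does not say that all patients enter the model.** This stands. A reader might infer that the document specifies an all-patient, single-term model. It does not: it is silent on the analysis set and the terms, and 'vortex intensity' could mean vortex patients only. The defect is under-specification, and the two readings answer different questions.

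**The largest rates rest on a high event rate.** This stands. The outcome is cause-specific, and the document gives no event rate. At 10% or 5% mortality without vortex the rates fall well below those at 25%, and at 5% with HR 2 they are close to nominal.

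**Recovering patients may not be in the model.** This stands in part. Recording stops at assisted ventilation, so patients who improve early have no day-14 value. The recovery route works only through those still passively ventilated on day 14. The vortex versus no-vortex route is unaffected.

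**Vortex status is largely a cut of the same pressure trajectory.** It has no threshold, so treating ΔΔP as one continuous severity scale is defensible, and a full jump in risk at the cut with no gradient above it is an extreme null. This supports keeping the all-patient model. It does not support calling its coefficient vortex intensity, because that model cannot tell a jump from a gradient.

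**The correction loses power.** This stands, as the power figures show, and it has to be reported with the result.

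**Conclusion.** The concern holds as a gap in specification with a real consequence for interpretation. If ΔΔP is fitted alone in all patients with both readings, a vortex versus no-vortex difference, or falling pressure in no-vortex patients still passively ventilated on day 14, can appear as an intensity effect. With 10 to 25% mortality without vortex and a vortex HR of 2 to 3, this happens in roughly 10 to 87% of studies of 60 to 100 patients, against about 5% within vortex patients. Every input except the significance level, the ΔΔP definition and day 90 is assumed. The mechanism follows from the definitions; the rates are illustrative.

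A reader might go further and infer that a significant coefficient will be an artefact, or that intensity has no effect. The document supports neither: it does not fix the analysis set, and the simulations assume the absence of an intensity effect without testing for it. The point should be fixed but does not invalidate the study, which is an observational cohort with no designated primary analysis.

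**What to change.** 1. State the analysis set and every term of the Cox model.
2. Report as the intensity analysis either ΔΔP in vortex patients only, or vortex yes/no together with intensity coded as ΔΔP in vortex patients and 0 in the others. ΔΔP plus a simple vortex indicator does not suffice.
3. Keep the all-patient ΔΔP model, but label it *change in driving pressure*.
4. Give the within-vortex hazard ratio with its confidence interval and number of deaths, and say that a non-significant result does not show absence of an intensity effect.
5. State the rule by which patients are classed as vortex, since the within-vortex analysis depends on it and the definition has no numeric cut-off.

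The cost is one extra term or a subset analysis, with no new data. The downside is a wide confidence interval and low power for the intensity estimate.
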